8.3.3 Safety Endpoints

Safety endpoints include AEs, clinical laboratory assessments, vital signs, and ECG parameters.

8.3.4 Exploratory Endpoints

Exploratory endpoints for Part A include

Exploratory endpoints for Part B include

CCI

8.4 Analysis Sets

The primary analysis population for all analyses of efficacy, safety, and health-related quality of life is the Safety population.

The Safety population will include all subjects who received at least 1 dose of trial treatment.

The Per-Protocol (PP) population will be the subset of the Safety population that is compliant with the protocol and excludes subjects with protocol violations. The protocol violation criteria will be outlined in the SAP. The per-protocol population will be used for additional sensitivity analyses for the primary and secondary efficacy endpoints.

Analysis of efficacy variables may also be performed on subgroups of interest and will be outlined in the Statistical Analysis Plan.

8.5 Description of Statistical Analyses

8.5.1 General Considerations

Full details of the planned analyses will be described in the trial SAP.

All data recorded during the trial will be presented in individual data listings performed on the Safety population. All data will be evaluated as observed, and no imputation method for missing values will be used unless otherwise specified in the SAP.

Descriptive statistics will be used to summarize the trial results, that is, statistics for continuous variables may include means, medians, ranges, and appropriate measures of variability. Qualitative variables will be summarized by counts and percentages. The uncertainty of estimates will be assessed by CIs. Unless otherwise specified, the calculation of proportions will be based on the sample size of the population of interest. Counts of missing observations will be included in the denominator and presented as a separate category if not otherwise specified in the SAP.

The estimation of PK parameters will be performed using WinNonlin® version 5.0 or higher. All other statistical analyses will be performed using SAS® version 9.2 or higher, or R (www.r-project.org), version 2.15.2 or higher.

8.5.2 Analysis of Primary Endpoint

Part A

The primary endpoint for Part A is the BOR according to RECIST 1.1, as determined by an IERC. For a BOR of PR or CR, confirmation of the response according to RECIST 1.1 (Eisenhauer 2009) will be required, preferably at the regularly scheduled 6-week assessment interval, but no sooner than 5 weeks after the initial documentation of CR or PR. Confirmation of PR can be confirmed

at an assessment later than the next assessment after the initial documentation of PR. A BOR of SD requires that a timepoint overall response of SD has been determined at a timepoint at least 6 weeks after start of study treatment. The response at each scheduled tumor assessment and the BOR will be listed for each subject. The number and proportion of BOR (defined as CR + PR) will be tabulated. The ORR will be determined as the proportion of subjects with a confirmed BOR of PR or CR.

The test statistic of the exact binomial test will be calculated and compared with the thresholds given in Section 8.1 to determine whether the null hypothesis of an $ORR \leq 20\%$ can be rejected at the interim analysis, or, if not rejected at the interim, at the primary analysis. The 2-sided 99.1% CI and the 95.9% CI will be constructed using the Clopper-Pearson method for ORR to form repeated CIs according to Jennison and Turnbull (Jennison 2000) at the interim analysis and primary analysis, respectively. The nominal p-value from the exact binomial test will also be reported.

Part B:

For Part B, the primary endpoint is durable response, defined as objective response (CR or PR) according to RECIST 1.1, determined by an IERC, with a duration of at least 6 months. Duration of response will be calculated as specified in Section 8.3.2. Subjects for whom the duration of response is censored will be treated as failures (successes) in the analysis of durable response if the censored duration of response is below (at least) 6 months, respectively. The number and proportion of subjects with a durable response will be tabulated. The DRR will be determined as the proportion of subjects with a durable response. The 95% CI for the DRR will be calculated using the Clopper-Pearson method. There will be 1 interim analysis at 3 months after the accrual of the 25th subject, with additional interim analyses possible. All interim analyses in Part B will be exploratory.

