7.1.2.1 Part A

During the treatment period, the following assessments will be performed (see [Appendix I](#) for the detailed schedule):

- The EQ-5D and FACT-M will be completed by subjects prior to any study related procedures at Week 7, and then once every 6 weeks thereafter while on treatment.
- Subject interviews (optional) by a trained experienced interviewer to collect subjects' current experience with their disease and its treatment (at Week 13 and at 6 months of treatment, see [Section 7.7.1](#)).
- AEs and concomitant medications will be documented at each trial visit.
- ECOG PS will be assessed at Day 1 (unless the Screening ECOG PS was performed within 3 days prior to Day 1) and at each study visit thereafter.
- Physical examinations will be performed at each treatment visit until Week 13 and every 6 weeks thereafter. Such examinations will include a comprehensive skin examination for tumor.
- Vital signs and body weight will be assessed in each treatment visit.
- A 12-lead ECG (assessed prior to infusion and 2 hours \pm 20 minutes after the end of infusion) will be assessed at each treatment visit up to and including Week 13, and every 6 weeks thereafter until 18 months, after which subjects no longer require on treatment ECGs.
- The laboratory hematology, hemostaseology will be assessed at each visit. Core serum chemistry tests will be assessed at Weeks 1, 7, 9, and 11 and after Week 13, every 2 weeks thereafter and full serum chemistry (including core chemistry) will be assessed at Weeks 3, 5, and 13 and then every 6 weeks thereafter. In addition, for subjects with liver metastases at Baseline, samples for ALT, AST, total bilirubin, and alkaline phosphatase determination will be collected at Weeks 2, 4, and 6. A basic urinalysis (dipstick) will be performed at each on treatment visit. If the basic urinalysis is abnormal, a full urinalysis should be performed.
- A urine β -HCG pregnancy test will be performed at each treatment visit (before each administration of the study drug) for females of childbearing potential.
- Tumor evaluation (see [Section 7.3](#)) will be performed at Week 7, and then once every 6 weeks thereafter, with a tumor assessment visiting time window of 5 days prior to dosing. After Week 55 (12 months) from the first treatment, tumor assessments will be every 12 weeks.

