7.1.2.2 Part B

During the treatment period, the following assessments will be performed (see [Appendix I](#) for the detailed schedule):

- The EQ-5D and FACT-M will be completed by subjects prior to any study related procedures at Week 7, and then once every 6 weeks thereafter while on treatment.
- Subject interviews (optional) by a trained experienced interviewer to collect subjects' current experience with their disease and its treatment (at Week 13 and at 6 months of treatment, see Section 7.7.1).
- AEs and concomitant medications will be documented at each treatment visit.
- ECOG PS will be assessed at Day 1 (unless the Screening ECOG PS was performed within 3 days prior to Day 1) and at each treatment visit thereafter.
- Physical examinations (directed to signs and symptoms) will be performed at each visit through Week 13 and then every 6 weeks thereafter. Such examinations may include a comprehensive skin examination for tumor.
- Vital signs and body weight will be assessed in each treatment visit (body weight may be collected within 3 days prior to infusion).
- The laboratory hematology, hemostaseology will be assessed at each treatment visit. Core serum chemistry tests will be assessed at each visit. A basic urinalysis (dipstick) will be performed on the Day 1 visit prior to administration of study drug. If the basic urinalysis is abnormal, then a full urinalysis should be performed. Urinalysis after Day 1 should be performed as clinically indicated.
- A urine or serum β -HCG pregnancy test according to local practice will be performed at Weeks 1, 5, 9, and 13 and then every 4 weeks thereafter for females of childbearing potential. Results of the most recent pregnancy test should be available prior to the next treatment.
- Tumor evaluation (see Section 7.3) will be performed at Week 7, and then once every 6 weeks thereafter, with a tumor assessment visiting time window of 5 days prior to dosing. After Week 55 (12 months) from the first treatment, tumor assessments will be every 12 weeks.
- PK samples will be collected from all subjects receiving avelumab within 2 hours prior to each study drug infusion through Week 7, every 6 weeks through Week 25, and then at 12-week

intervals thereafter while on treatment. Post study drug administration samples will be collected at the end of infusion at Weeks 1, 7, and 25.

- Free T4, and TSH will be measured at Week 1, Week 7, Week 13, and every 6 weeks during the treatment period.

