16.1 Primary Endpoint Analyses

Analysis sets: ITT analysis set, PP analysis set

The primary endpoint is the confirmed BOR to therapy in terms of either CR or PR according to RECIST 1.1 (Appendix I), as determined by an IERC. The tumor response will be based on the IERC assessment of overall response at each time point. In case of different dates of scans within the same tumor assessment visit, the earliest scan date should be used as the date of tumor assessment.

The confirmed BOR is defined as the best response obtained among all tumor assessment visits after start of trial treatment until documented disease progression, excluding assessments after start of subsequent anticancer therapy, taking requirements for confirmation into account as detailed below. The confirmed ORR will be defined as the proportion of subjects with a confirmed BOR of PR or CR.

A separate Imaging Data Management Plan and Data Transfer Plan will be created to summarize the details of the data structure and data delivery schedule of IERC assessment results.

The following requirement is taken into account for confirmation of response:

- PR or CR needs to be confirmed at a subsequent tumor assessment, preferably 6 weeks after the initial observation of response and according to the normal 6-week assessment schedule but no sooner than 5 weeks after the initial documentation of CR or PR.
- PR can be confirmed at an assessment later than the next assessment after the initial documentation of PR.
- The minimum duration for a BOR of SD is defined as at least 6 weeks after start of study treatment.

Table 2 summarizes the derivation rules described by [Eisenhauer, et al.](#) for the BOR when conformation from subsequent assessment is needed (5).

Table 2 Best overall response when confirmation of CR/PR is required

| Overall response 1st time point | Overall response subsequent time point | Best overall response (BOR) |
|---------------------------------|--|-----------------------------|
| CR | CR | CR |
| CR | PR | SD, PD or PR ^a |

| Overall response 1st time point | Overall response subsequent time point | Best overall response (BOR) |
|--|---|---|
| CR | SD | SD provided minimum criteria for SD duration met; otherwise, PD |
| CR | PD | SD provided minimum criteria for SD duration met; otherwise, PD |
| CR | NE | SD provided minimum criteria for SD duration met, otherwise NE |
| PR | CR | PR |
| PR | PR | PR |
| PR | SD | SD |

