- New anticancer therapy started before first post-baseline assessment
- SD of insufficient duration (tumor assessment <6 weeks after start date without further evaluable tumor assessment)

The primary endpoint analysis will be repeated for the PP analysis set as a sensitivity analysis if the PP analysis set includes less than 95% of subjects in the ITT analysis set. The ORR will be calculated along with the two-sided 95% Clopper-Pearson CIs.

According to Section 5.3.1 Inclusion Criteria of the clinical protocol, all subjects who are enrolled to the study to receive at least one dose of avelumab should have measurable disease at baseline by RECIST 1.1 according to investigator assessments. However, it is possible that a subject in the ITT analysis set could be found to have no measurable disease at baseline per IERC assessment, and would not have a response in the primary endpoint analysis. Therefore the primary endpoint analysis will be repeated on subjects with measurable disease at baseline per RECIST 1.1 by the IERC as a sensitivity analysis. The ORR will be calculated along with the two-sided 95% Clopper-Pearson CIs.

The response at each scheduled tumor assessment and the BOR will be listed for each subject.

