- Subject has a tumor assessment > 5 weeks after first dose of study treatment (unless PD or death is observed before that time, in which case the subject will not be excluded from the PP analysis set).

The PP analysis set will be used for additional sensitivity analyses for the primary and secondary efficacy endpoints. If the PP analysis set includes at least 95% of subjects in the safety analysis set, additional efficacy analyses on the PP analysis set will be omitted as the differences in the results based upon these two analysis sets are expected to be negligible.

Subgroup Analysis Sets

The below subgroup analyses will be performed on primary and key secondary efficacy endpoints. Since the study is not powered for any subgroup analysis, CCI.

The following subgroups will be defined:

- Age Group 1:
 - Age < 65 years (Reference)
 - Age \geq 65 years
- Age Group 2:
 - Age \leq Median (Reference)
 - Age > Median
- Gender
 - Male (Reference)
 - Female
- Race
 - Caucasian / White (Reference)
 - Asian
 - Black/ African American
 - Other
- Pooled Geographical Region:
 - North America
 - Europe (Reference)
 - Asia
 - Rest of the World (Australia and/or Latin America will be included as additional pooled geographical regions if including \geq 10 subjects in the FAS)

CCI

CCI

- Time from initial diagnosis to study entry
 - ≤ 3 months (Reference)
 - > 3 months and ≤ 1 year
 - > 1 year
- Time from first occurrence of metastatic disease to study entry
 - ≤ 3 months (Reference)
 - > 3 months and ≤ 1 year
 - > 1 year
- ECOG PS at baseline
 - ECOG PS 0 (Reference)
 - ECOG PS 1
- Disease Burden by IERC assessment
 - Baseline SLD \leq Median (Reference)
 - Baseline SLD $>$ Median
- Presence of visceral metastases at baseline. Target or non-target lesions that are categorized as neither skin (including soft tissue and eye) nor lymph node lesions per IERC assessment are classified as visceral metastases.
 - Present
 - Absent (Reference)
- Number of prior systemic chemotherapies
 - 0 Prior Therapy (Reference)
 - ≥ 1 Prior Therapies

- Site of primary tumor (representing known versus unknown primary status)
 - Skin
 - Non-Skin (Reference)
- Lymph node disease only at Baseline per IERC assessment
 - Yes (Reference)
 - No
- Baseline CD8 T-cell density (expressed in % CD8+ cells and number of CD8+ cells/mm²)
 - < Median (Reference)
 - ≥ Median

11 General Specifications for Statistical Analyses

Data handling after cut-off date:

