16.2.2 Best Overall Response and Objective Response

The confirmed BOR is defined as the best confirmed response obtained among all tumor assessment visits after start of study treatment until documented disease progression, taking requirements for confirmation into account as detailed in [Section 16.1.1](#). In addition, the minimum duration for a BOR of SD is defined as at least 6 weeks after start of study treatment. A BOR of PD requires that progression is observed ≤ 12 weeks after first dose of study treatment (and not qualifying for CR, PR or SD).

Only tumor assessments performed before the start of any further anti-cancer treatment will be considered in the assessment of BOR. Clinical deterioration will not be considered as documented disease progression. If a tumor assessment was performed on the same day as the start of a new anti-cancer therapy, it is assumed that the tumor assessment was performed prior to the start of the new anti-cancer therapy; therefore, this tumor assessment is included in the assessment of BOR.

The tumor response at each assessment visit will be determined according to RECIST 1.1 and as adjudicated by an IERC. In case of different dates of scans within the same tumor assessment visit, the date of assessment is determined by the IERC as specified in the Charter.

The objective response rate (ORR) is defined as the proportion of subjects having reached a confirmed BOR of CR or PR according to RECIST 1.1 and as determined by the IERC.

[Table](#) summarizes the derivation rules described by [Eisenhauer, et al.](#) for the BOR when confirmation from subsequent assessment is needed (5).

Table 3 Best Overall Response When Confirmation of CR/PR Is Required

| Overall response 1st time point | Overall response subsequent time point | Best overall response (BOR) |
|------------------------------------|---|---|
| CR | CR | CR |
| CR | PR | SD, PD or PR ^a |
| CR | SD | SD provided minimum criteria for SD duration met; otherwise, PD |
| CR | PD | SD provided minimum criteria for SD duration met; otherwise, PD |
| CR | NE | SD provided minimum criteria for SD duration met, otherwise NE |
| PR | CR | PR |
| PR | PR | PR |
| PR | SD | SD |
| PR | PD | SD provided minimum criteria for SD duration met, otherwise, PD |
| PR | NE | SD provided minimum criteria for SD duration met, otherwise NE |
| NE | NE | NE |

CR = complete response, PR = partial response, SD = stable disease, PD = progressive disease, NE = non-evaluable.

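### The 6-week minimum for a best response of stable disease falls on the nominal first-scan day and ignores the 5-day early scan window; only the SD/PD/NE split among non-responders is affected

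*Protocol*

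**What the plan says.** **The minimum.** Protocol 8.5.2 requires for a BOR of SD that "a timepoint overall response of SD has been determined at a timepoint at least 6 weeks after start of study treatment". Part A SAP 16.1 says: "The minimum duration for a BOR of SD is defined as at least 6 weeks after start of study treatment". Part B SAP 16.2.2 has the same rule: "the minimum duration for a BOR of SD is defined as at least 6 weeks after start of study treatment". None of the three gives a tolerance.

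**The schedule.** Protocol 7.1.2.2 (Part B) says: "Tumor evaluation (see Section 7.3) will be performed at Week 7, and then once every 6 weeks thereafter". Section 7.1.2.1 sets the same timing for Part A. Both sections give the scan a window that runs backwards only, "with a tumor assessment visiting time window of 5 days prior to dosing". Protocol 7.1.2 also allows 3 days before to 1 day after the scheduled visit day for all trial procedures.

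**What happens when the minimum is missed.** In the BOR tables of both SAPs (Part A Table 2, Part B Table 3), an unconfirmed CR or PR followed by PD counts as SD if the minimum is met and as PD otherwise. If followed by a non-evaluable assessment, it counts as SD or otherwise NE. Part A SAP 16.1 lists as a reason for NE "SD of insufficient duration (tumor assessment <6 weeks after start date without further evaluable tumor assessment", and Part B SAP 16.2.2 has an equivalent reason. Part B SAP 16.2.2 also requires progression within 12 weeks of first dose for a BOR of PD, lists later progression with no evaluable scan in between as NE, and assigns the combination of early SD and late PD to NE because the SD came too early.

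**The concern.** The minimum is set at the exact nominal day of the first scan, while the protocol lets sites scan earlier but grants no matching later days through the scan window itself. A site that follows the plan can therefore produce an SD reading that the analysis rule rejects. Two subjects with the same disease course can then fall into different BOR categories because of the permitted day on which the scan was booked. The effect has one direction: SD is understated, and PD or NE overstated.

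Confirmed BOR is the named primary endpoint of Part A and a secondary endpoint of Part B, and both SAPs tabulate SD, PD and NE and break NE down by reason. At stake is whether that table reflects disease or scheduling.

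**Working it through.** **Inputs.** Day 1 is the day of first dose (Section 11 of both SAPs). The planned day of Week X is (X − 1) × 7 + 1 (Part B SAP Section 11). Elapsed days = study day − 1. The SD minimum is 6 × 7 = 42 days. The Part B limit for PD is 12 × 7 = 84 days.

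**The plan's own days.** Week 7: (7 − 1) × 7 + 1 = Day 43. Week 13: (13 − 1) × 7 + 1 = Day 85. Both match the Schedule of Assessments in Protocol Appendix I. Day 43 is 43 − 1 = 42 days after first dose, exactly the minimum.

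**First scan.** With dosing on Day 43, the window is Days 38 to 43.

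| Scan day | 38 | 39 | 40 | 41 | 42 | 43 |
|---|---|---|---|---|---|---|
| Elapsed days | 37 | 38 | 39 | 40 | 41 | 42 |
| At least 42? | no | no | no | no | no | yes |

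The share of permitted days that fail depends on the reading:
- Elapsed days, nominal window (Days 38 to 43): 5 of 6.
- Part A SAP Section 11 computes durations as the difference plus 1 unless otherwise specified. Day 42 then counts as 42 − 1 + 1 = 42 days and passes: 4 of 6 fail.
- Adding the +1-day visit window allows Day 44 (43 elapsed days, passes): 5 of 7 fail.
- Adding the −3-day visit window as well allows dosing on Day 40 and a scan on Day 35 (34 elapsed days). The permitted range is then Days 35 to 44, and Days 35 to 42 fail: 8 of 10.

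**Second scan.** The nominal Week 13 window, Days 80 to 85, is 79 to 84 elapsed days. SD there clears the 42-day minimum, and PD there is within Part B's 84-day limit. Day 86, allowed by the +1-day visit window, is 85 elapsed days and misses that limit.

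**Effect on one disease course in Part B: SD at scan 1, PD at scan 2.**

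| Scan 1 | Scan 2 | BOR |
|---|---|---|
| Day 43 | Day 85 | SD |
| Day 40 | Day 85 | PD |
| Day 40 | Day 86 | NE, classed as SD too early |

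All three pairs are permitted; the third uses the +1-day visit window.

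**Who is affected.** BOR changes only if SD, or an unconfirmed CR or PR, rests on scan 1 alone and is followed by PD or by no further evaluable scan. SD still present at Week 13 gives a BOR of SD. PR followed by SD gives SD in both tables with no duration condition.

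**What does not move.** ORR counts confirmed CR and PR, and DRR counts responses lasting at least 6 months. Duration of response, PFS and OS do not use the SD minimum. The Part A design figures for 84 subjects reproduce (0.0045 and 0.0214 nominal, 0.0225 overall, power 87.2% at a true ORR of 35%), and none depends on the SD rule.

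**Tolerances elsewhere.** CR and PR may be confirmed from 5 weeks against a 6-week schedule. The Part B per-protocol set (Part B SAP Section 10) asks only: "Subject has a tumor assessment > 5 weeks after first dose of study treatment". A Part B subject whose only post-baseline scan is SD on Day 38 meets that criterion (37 > 35 days) but has a BOR of NE.

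**The case against.** The strongest reply is that nothing inferential or decision-relevant depends on this. SD, PD and NE are all non-responses, the exposure-response analyses in both SAPs group them together, and no readable text defines an estimate that counts SD as benefit. The 6-week minimum is identical in the protocol and both SAPs, so the documents do not contradict each other on the rule. The NE breakdown by reason shows early SD without a later evaluable scan, the protocol calls for a listing of responses by assessment, and Part B SAP 16.2.2 already foresees early SD with late PD and treats it as rare. The 5-week per-protocol criterion governs membership of an analysis set, not the meaning of SD.

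Most of this stands, and it sets the severity at minor. Two parts do not remove the point. The NE breakdown cannot show early SD followed by timely PD, because that subject is counted as PD; the case can be recovered only by reading the listing. And the combination that Part B treats as rare can arise from permitted scheduling.

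A reader might infer that SD found on schedule is generally turned into PD or NE. The documents do not support that: a later qualifying scan restores SD. A reader might also infer that 83% (5 of 6) of first scans fail, or derive a count of reclassified subjects. That share assumes scan days spread evenly over Days 38 to 43 and leaves out the +1 day used to reach Day 86. Neither the distribution of scan days nor the share of subjects whose SD rests on scan 1 alone is given.

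**Conclusion.** The mismatch is real and minor. The SD minimum equals the nominal first-scan day, so most permitted scan days cannot support SD on any of the readings above. Only the descriptive SD/PD/NE split of BOR changes. ORR, DRR, duration of response, PFS, OS and the Part A type I error and power are untouched; a reader who took this as a threat to the primary result in either part would go beyond the documents. The number of subjects affected cannot be computed from them.

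The conclusion assumes that the 6-week rule is applied literally and that the IERC charter, which is not supplied, adds no tolerance; nothing in the protocol or SAPs suggests that it does. The Day 86 edge in Part B also assumes that the general visit window applies to scans, which Protocol 7.1.2 indicates by covering all trial procedures.

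**What to change.** **Part B, prospectively, in SAP 16.2.2:**
- Count SD at the scheduled Week 7 assessment when that scan is within its permitted window. For the nominal window this is a minimum of 37 days after first dose (Day 38). If the −3-day visit window is also meant to apply, it is 34 days (Day 35). The SAP should state which, because 37 days would still reject Days 35 to 37.
- Let PD at the Week 13 scan count through Day 86.
- Align the two NE reasons (SD of insufficient duration, and PD too late) with these limits.
- Keep the 6-week version as a sensitivity tabulation.
- Carry the same wording into Protocol 8.5.2 for Part B if the protocol is amended again.

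**Part A:** leave the rule as it is. The protocol cites the Part A results as published (10.6.2), so loosening the rule now would be a post hoc change in the favourable direction. Add the aligned version only as a supplementary tabulation, labelled as such.

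**Cost:** a sentence in the Part B SAP, a changed programming constant and one extra table. SD becomes 42 − 37 = 5 days more lenient, or 42 − 34 = 8 days if the visit window is included.
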